SECONDARY OBJECTIVES	To evaluate rates of late (> 3 months after treatment) gastrointestinal toxicity following fractionated Linac based SBRT for pancreatic tumors. Toxicities of note include grade 2 or greater gastritis, enteritis, fistula, or ulcer and any other grade 3 or greater gastrointestinal toxicity. To evaluate local progression free survival, overall survival and metastasis-free survival rates after Linac based SBRT and subsequent resection in patients with resectable and/or borderline resectable pancreatic adenocarcinoma of the head and/or body. To develop and standardize Linac based SBRT delivery and dosimetric parameters. To estimate resection margin positivity (R0/R1) and pathologic complete response rate after neoadjuvant SBRT To evaluate pre- and post- SBRT patient reported quality of life (QOL)
TREATMENT	After 3- 4 months of chemotherapy, patients will be enrolled to a single arm trial of stereotactic body radiotherapy (SBRT) in 5 fractions given over 15 days. They will then proceed to surgery after a break of 4-6 weeks.

INCLUSION CRITERIA	
 • Age >18 years. • Karnofsky Performance Status >70% (see Appendix IV). • Histologically confirmed pancreatic adenocarcinoma of the head and/or body; at least the majority of the histopathologic specimen must be identified as adenocarcinoma. • Pancreatic tumors must be considered at least borderline resectable and/or borderline resectable at time of treatment planning. Definition of resectable and/or borderline resectable: no metastases, less than 180 degree involvement of hepatic artery, superior mesenteric artery or celiac artery • No active infection requiring hospitalization • If bilirubin > 2, patients must have a biliary stent placed prior to SBRT. • Patients must have acceptable organ and marrow function (see section “Inclusion Criteria, page 17-18). • Women who are not post-menopausal (as defined in Appendix V) should have a negative urine or serum pregnancy test. Women of childbearing potential must agree to use adequate contraception for the duration of study participation. • Ability to understand and the willingness to sign a written informed consent document. • Life expectancy > 3 months. • Patients are to have received neoadjuvant chemotherapy prior to enrollment. Approved regimens may consist of 3-4 months of gemcitabine-based chemotherapy or FOLFIRINOX. Patients will have a 2-4 week break between last chemotherapy administration and start of

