positive for asTF was significantly higher compared to that in all other cohorts ($p<0.01$, Chi-Square test). The mean asTF concentrations in the cohorts were as follows: PDAC, 0.403 ± 0.912 ng/mL; healthy subjects, 0.169 ± 0.596 ng/mL; the differences between mean asTF levels in the cohorts did not reach significance. Next, we evaluated asTF's potential as a biomarker to help detect a more aggressive PDAC phenotype. Among the 43 patients with PDAC, 36 were initially deemed resectable and 7 unresectable due to the presence of metastatic disease as determined by diagnostic screening; following exploratory laparoscopic surgery, 11 out of 36 patients initially deemed resectable were deemed unresectable due to the presence of metastatic disease. When the entire PDAC cohort was split into bona fide resectable (25) and unresectable (18) sub-cohorts, positivity for asTF was significantly more prevalent in the unresectable sub-cohort irrespective of the results of initial evaluation and/or pre-operative CA19-9 levels (asTF ≥0.2 ng/mL: 13 unresectable and 7 resectable patients; asTF <0.2 ng/mL: 5 unresectable and 18 resectable patients, $p=0.0059$, Fisher's exact test).

Our findings suggest that asTF at levels ≥0.2 ng/mL occurs more frequently in the plasma of patients with PDAC compared to healthy subjects. Further, PDAC patients whose plasma asTF levels were equal to or exceeded 0.2 ng/mL had a significantly lower chance to qualify for tumor resection, irrespective of initial pre-surgical diagnostic evaluation. asTF may thus comprise a novel marker of aggressive PDAC phenotype with potential utility in patient stratification, warranting prospective evaluation of larger PDAC patient cohorts.

Proposed research: prospective evaluation of asTF levels in circulation of patient with PDAC at 3 time points pre / post-SBRT (time point 0-14 days before surgery) and post-operative. Blood will be drawn in 3 ml sodium citrate tubes, ~1.5 ml of platelet poor plasma isolated, frozen until use, and assayed for asTF using ELISA as described above. We hypothesize that asTF levels will i) drop post-SBRT, ii) further drop post-resection, and iii) rise either concomitantly or shortly before recurrence. We also hypothesize that higher asTF levels at the onset and/or during the study will positively correlate with more aggressive disease and, consequently, poorer response to treatment.

XII. MEASUREMENT OF EFFECT

Anti-tumor Effect

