APPENDIX I

STUDY CALENDAR

	Pre-Study	Pre-SBRT ⁸	SBRT Treatment ^{9,10}	Follow-Up ⁵ (Post-Radiation Treatment)					
				4-6 weeks	4 mos	6 ³ mos	9 mos	12 ³ mos	Yrs 2-5 Q 3-6 mos
Initial Consult	X								
Demographics	X								
History / Physical Exam	X			X	X	X	X	X	X
Informed consent	X								
Biopsy (confirmed adenocarcinoma)	X								
Labs: CBC, CMP, CA19-9		X ⁶		X	X	X	X	X	X
Post-op complication assessment (appendix 6)				X					
Negative Pregnancy Test ⁷		X							
Seed Placement (EUS, CT, intraoperatively)		X							
Simulation Scan		X							
Radiologic Evaluation (CT)		X		X ²	X	X	X	X	X
QoL Questionnaire		X		X	X ⁴	X	X ⁴	X	X
AE Evaluation	X			X	X	X	X	X	X
Research tubes		X		X ¹¹					

1 - CT pancreas or chest/abdomen/pelvis, as per treating physician, required pre- and post-SBRT.
 2 - If being reevaluated for resection, scans will be conducted at 4-6 weeks or as determined necessary by treating physician.
 3 - It is preferred that patients have the 6MFU and 12MFU evaluation and imaging at the treating institution. Other evaluations may be done at a local center however records must be submitted to SBRT treating facility.
 4 - QoL questionnaires may be completed and returned by mail if preferred.
 5 - Follow-up appointments have a +/- 30 day tolerance window. (ex. 6MFU may occur between 5-7 months)
 6 - Pre-SBRT labs should be done within 2 weeks prior to treatment.
 7 - Pregnancy test by urine or serum, for women who are not post-menopausal as defined in Appendix III.
 8 - Pre-SBRT procedures should be completed within 45 days of beginning treatment.
 9 - It is recommended that patients discontinue any chemotherapy one week prior to SBRT
 10 - Ideally all 5 fractions should be delivered Monday through Friday; however, treatment may be delivered over 2 weeks, as long as the patient receives at least 2 fractions per week.
 11- Pre-surgery

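### Section XI plans a post-operative asTF blood sample that the study calendar does not schedule; separately, the recurrence hypothesis cannot be properly tested with the samples in either place.

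*Combined protocol and SAP*

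**What the plan says.** Section XI (Correlative Studies, asTF) proposes measuring plasma asTF "at 3 time points pre / post-SBRT (time point 0-14 days before surgery) and post-operative". I read this as three draws: before SBRT, after SBRT within the two weeks before surgery, and after surgery. No day or window is given for the last. The assay needs its own tube ("Blood will be drawn in 3 ml sodium citrate tubes"), from which platelet-poor plasma is isolated and frozen for ELISA.

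The same paragraph states three numbered hypotheses, that asTF will i) "drop post-SBRT, ii) further drop post-resection, and iii) rise either concomitantly or shortly before recurrence". It adds an unnumbered one, that "higher asTF levels at the onset and/or during the study will positively correlate with more aggressive disease".

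In Appendix I, the row "Research tubes" is marked in the Pre-SBRT column and in the 4-6 week column. The second mark carries footnote 11: "11- Pre-surgery". The columns for 4, 6, 9 and 12 months and for years 2-5 are empty in that row, although the routine laboratory row is marked in all of them.

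**The concern.** The text and the calendar disagree on how many research draws there are, and the draw missing from the calendar is the only one after resection. The calendar is the document that visits are likely to be run from. Section X (Monitoring Plan) also has the DSMB audit follow-up against it, so an audit would not pick up the omission. Plasma that was not drawn cannot be recovered later.

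The second problem does not depend on the calendar. A hypothesis about when asTF rises relative to recurrence needs repeated values during follow-up, and Section XI does not plan them.

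**Working it through.** No sample size, power or error rate underlies this point, and the plan gives no figure to reproduce. The check sets the two places side by side and matches each hypothesis to the samples it needs.

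**Step 1: count the draws.** Section XI: 3 (pre-SBRT, post-SBRT before surgery, post-operative). Appendix I: 2 (pre-SBRT, 4-6 weeks marked as before surgery). Difference: 3 − 2 = 1, the post-operative draw.

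**Step 2: confirm what the second calendar mark is.** The Synopsis says of patients after SBRT: "They will then proceed to surgery after a break of 4-6 weeks". A 4-6 week visit held before an operation at 4-6 weeks precedes it by at most 6 − 4 = 2 weeks. That agrees with the 0-14 day window in Section XI. The second mark is therefore the post-SBRT sample. The column also holds the post-operative complication assessment, but footnote 11 places the research tube before surgery.

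**Step 3: look for the draw elsewhere.** The follow-up text in Section IV lists blood count, chemistry, tumor markers and quality of life at each visit, and no citrate tube. The optional banking in Section IV concerns tissue. I found no other place that schedules the post-operative sample.

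**Step 4: match hypotheses to samples.**

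| Hypothesis | Needs | Section XI draws | Appendix I draws |
|---|---|---|---|
| i) fall after SBRT | pre-SBRT, pre-surgery | yes | yes |
| ii) further fall after resection | pre-surgery, post-operative | yes | no post-operative value |
| iii) rise with or before recurrence | a post-operative level and later values near recurrence | no: one undated post-operative draw | no |
| Unnumbered: level and aggressive disease | baseline and/or later level | yes | yes |

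Moving from Section XI to Appendix I changes only the row for ii. The row for iii fails in both columns: a rise needs at least two values after resection, and Section XI plans one.

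**Step 5: size.** A post-resection sample exists only for resected patients. The ceiling is 20 (maximum enrollment in Section IX). The completion rule in Section IX passes with 6 of 20 completing therapy with an R0 or R1 resection. In a trial that passes that rule, the samples at stake therefore number from about 6 to 20, one per resected patient.

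**Step 6: why the mark needs a window.** Calendar visits are timed from radiation, not from surgery. The next column after 4-6 weeks is 4 months, or 4 × 30.4 / 7 = 17.4 weeks. With surgery at 4-6 weeks, that visit falls 17.4 − 6 = 11.4 to 17.4 − 4 = 13.4 weeks after the operation. The 30-day tolerance (4.3 weeks) widens this to about 7.1 to 17.7 weeks. A mark placed there without a window would mix quite different intervals after resection.

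**The case against.** The strongest reply is that Section XI is itself protocol text, calls for the post-operative draw, and is not overridden by anything in Appendix I. This stands. A reader might infer that the sample will certainly not be taken and that there will be no post-resection data; the documents do not show that. They show a contradiction, with a loss that follows if the calendar is what staff follow.

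A reader might also infer that the calendar gap makes two of the three numbered hypotheses untestable. It does not. The gap accounts for hypothesis ii only. A calendar that matched Section XI exactly would still leave iii without the serial samples it needs. Hypothesis i and the unnumbered correlation hypothesis can be addressed with the two scheduled draws.

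A third tempting reading is that a third of all planned samples would be lost: 20 of 20 × 3 = 60. That assumes every patient is resected. The completion rule allows far fewer, and in the preliminary cohort described in Section XI, 11 of 36 patients first judged resectable proved not to be.

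It can also be said that the work is exploratory. asTF is not among the objectives in Section I and has no endpoint or analysis in Section IX, and Section XI leaves funding to pending grants or center support. That is correct and limits the importance of the point. It does not remove the contradiction, and the small number of resected patients makes each lost sample count for more.

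Last, a mark could have been lost from the calendar in the text I read, since footnote 1 has no visible anchor in the table. Footnote 11 did survive, and only two marks appear in the row, so this lowers confidence only slightly.

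**Conclusion.** The point holds as two separate statements. First, Section XI and Appendix I conflict: three asTF draws are planned and two are scheduled, and the unscheduled one is the only draw after resection. If the calendar is followed, hypothesis ii has no post-resection value in the resected patients, at most 20 and possibly as few as 6 in a trial that passes its completion rule. Second, hypothesis iii cannot be properly tested under either part of the protocol, because no serial follow-up samples are planned.

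The first statement assumes that the calendar row is complete as it appears and that staff work from it. The second rests on Section XI alone. Neither reaches the primary endpoint, the secondary objectives or any stopping rule, so this is a correction worth making to an exploratory study and not a threat to the trial's conclusions.

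**What to change.** Reconcile the two places:

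- Add a post-operative research-tube mark to Appendix I. Time it from the date of surgery, state a window, and put the same window in Section XI. Have it drawn where the plasma can be isolated and frozen; footnote 3 of the calendar allows visits other than those at 6 and 12 months to take place at a local center.
- Delete hypothesis iii, or label it as not testable with the planned samples. Keep it only if the sponsor chooses to fund further citrate tubes and ELISA assays at follow-up visits.

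The first change costs a calendar amendment submitted to the IRB and one 3 ml tube per resected patient, with an assay that Section XI already plans. If the draw is tied to a visit with routine blood work, no extra venepuncture is needed. Deleting or relabelling hypothesis iii costs only the text change. Serial sampling for iii would add assays beyond the three per patient in Section XI, plus processing at visits that may be held elsewhere, so it is the more expensive choice.

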--------------------	--

EXCLUSION CRITERIA	
 • Presence of metastatic disease. • Infections requiring systemic antibiotic treatment. • Unable to understand or unwilling to sign a written informed consent document. •
PROCEDURES	Endoscopically guided fiducial placement with optional biopsies obtained at the time of fiducial placement.
STATISTICAL CONSIDERATIONS	See statistics section.

SCHEMA

Eligibility: resectable or borderline resectable adenocarcinoma of the pancreas. Definition of resectable: no metastases, less than 180 degree involvement of hepatic artery, superior mesenteric artery or celiac artery

I. OBJECTIVES

Primary Objective

- To evaluate rates of acute (within 3 months of treatment) grade 3 or greater gastrointestinal toxicity.

Secondary Objectives

- To evaluate rates of late (> 3 months after treatment) grade 2 gastritis, enteritis, fistula, and ulcer, or any other grade 3 or greater gastrointestinal toxicity
- To determine rates of local progression free survival, overall survival, and metastasis- free survival in patients with resectable and/or borderline resectable pancreatic adenocarcinoma of the head and/or body undergoing neoadjuvant SBRT
- To evaluate patient quality of life before and after Linac based SBRT.
- To evaluate the margin positivity rate and pathologic complete response rate after Linac based SBRT.
- To further develop standardization of Linac based SBRT delivery and dosimetric parameters.

II. BACKGROUND

Natural History and Management of Pancreatic Cancer

More than 40,000 individuals are diagnosed with pancreatic cancer annually in the United States. Despite aggressive combined modality treatment approaches, five-year survival of patients with pancreatic cancer is still less than 5% (1). Clearly, more innovative treatments are needed to improve survival in this group of patients.

Surgical resection is considered to be the only potentially curative treatment option (2). However, the majority of pancreatic cancer patients do not have resectable and/or borderline resectable disease at presentation. More than 85% of patients have locally advanced or metastatic disease when initially diagnosed.

Current Adjuvant Management of Resectable and/or borderline resectable Pancreatic Adenocarcinoma

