Patients will be evaluated for anti-tumor effect by follow-up imaging (pancreas protocol CT and/or PET-CT imaging) as outlined above. All subsequent scans (post-treatment) will be compared to the same pretreatment CT that was used in conjunction with radiation treatment planning.

Patients will be evaluable for toxicity and evaluable for objective response at the follow-up intervals specified above.

Disease Parameters

Pancreatic tumor response will be based upon standard radiographic criteria for the treated lesion and will be prospectively recorded in the UC secure database. Radiographic response of the pancreatic tumor by diagnostic CT scans will be defined according to RECIST criteria as described below:

- CR = complete disappearance of index lesion
- PR = at least 30% decrease in the longest diameter of the index lesion
- PD = more than 20% increase in the longest diameter of the index lesion
- SD = does not meet criteria for PR or PD

Local tumor progression will be defined as $\geq20\%$ increased size on CT scan compared to a CT

scan from prior to treatment. Distant progression will be defined as any new tumor found outside of the pancreas or periampullary region on CT scan. Local and/or distant progression will be evaluated by both PET/CT (if available) and CT scan as deemed by treating physician.

Methods for Evaluation of Measurable Disease

Pancreas protocol CT scans (biphasic imaging, 1.25 mm cuts) and/or FDG PET-CT scans (optional and if recommended by the treating physician) will be obtained at all follow-up intervals as described in the treatment calendar.

XIII. RESPONSE CRITERIA

Evaluation of Target Lesions

Patients' responses to therapy will also be evaluated clinically after completion of their Linac based SBRT. The following are clinical definitions for response:

- CR = complete alleviation of pain or other symptoms thought to be related to the index lesion
- PR = improvement, but not complete elimination, of pain or other symptoms thought to be related to the index lesion
- PD = worsening of pain or other symptoms thought to be related to the index lesion SD = does not meet criteria for PR or PD
- Radiographic response will be defined as outlined in section 11.1.2.

Evaluation of Non-Target Lesions

Standard radiographic criteria will be utilized for non-target lesions. Any disease outside of the pancreas region will be considered metastatic disease. If possible a biopsy should be obtained to confirm metastasis.

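### Local progression is measured from the pre-treatment CT at every visit, so in an unresected patient whose tumor shrinks after SBRT, regrowth must first use up the shrinkage before it counts

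*Combined protocol and SAP*

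**What the plan says.** Section XII fixes the comparator twice. Under Anti-tumor Effect: "All subsequent scans (post-treatment) will be compared to the same pretreatment CT that was used in conjunction with radiation treatment planning". Under Disease Parameters, the paragraph beginning "Local tumor progression will be defined as" sets the threshold at an increase in size of 20% or more on CT, again relative to a scan taken before treatment.

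The radiographic response list in the same section gives "PR = at least 30% decrease in the longest diameter of the index lesion" and "PD = more than 20% increase in the longest diameter of the index lesion". Neither bullet names its own reference scan, so the general comparison rule applies to both. The list is introduced as RECIST as set out there, but nothing in it, or elsewhere in the documents, refers to the smallest size reached.

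Three places depend on this rule or may do so:

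- The Synopsis lists as a secondary objective "To evaluate local progression free survival, overall survival and metastasis-free survival rates after Linac based SBRT", and Section I repeats it.
- Section XIII, Duration of Response, ends the response at the first sign of local progression or of new metastasis.
- Section IX, Supplementary Analysis Plans, analyses time from registration to locoregional recurrence by Kaplan-Meier. It does not define recurrence or cite the 20% threshold.

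**The concern.** A fixed pre-treatment reference suits the question of how much a tumor has responded. It suits the question of whether the tumor is growing again less well. If the lesion shrinks after SBRT, the shrinkage becomes a credit that later growth must use up before the 20% threshold starts to bite. The better the initial response, the larger the credit, so the definition is least sensitive in the patients in whom SBRT first worked.

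This matters where the treated lesion stays in place, because there the percentage rule can be applied throughout follow-up. Local progression-free survival and duration of response would look better in those patients than a rule anchored at the smallest size would show. The Background section cites local control rates from other SBRT series (83% at one year in one, above 90% in another), and readers are likely to set this trial's figure beside them.

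**Working it through.** The plan states no event count, power or target for local progression, so it has no figure on this point to reproduce. The one related set of figures is in the Completion of Therapy Stopping Rules, which bound the number of patients without a completed resection. With 20 patients and failure at 5 or fewer completers, the binomial probability of failure is 0.804 at a true rate of 20% (plan: more than 80%) and 0.126 at 40% (plan: less than 13%). Both agree.

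**Inputs (Section XII).** Progression threshold: 1.20 times the pre-treatment size. Partial response: 0.70 times the pre-treatment size or less. Longest diameter is taken as the measure, as in the response list.

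**Formulas.** Let x be the largest fractional shrinkage from baseline.

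- Plan's rule: event at 1.20 × baseline. Regrowth needed from the smallest size = 1.2/(1-x) - 1.
- Smallest-size rule: event at 1.20 × (1-x) × baseline. Regrowth needed = 20%.

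| Shrinkage x | Regrowth needed, plan | Event as % of baseline, plan | Event as % of baseline, smallest-size rule |
|---|---|---|---|
| 0% | 20% | 120% | 120% |
| 10% | 1.2/0.90 - 1 = 33% | 120% | 108% |
| 20% | 1.2/0.80 - 1 = 50% | 120% | 96% |
| 30% (PR) | 1.2/0.70 - 1 = 71% | 120% | 84% |
| 50% | 1.2/0.50 - 1 = 140% | 120% | 60% |

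**Worked case (assumed 30 mm at baseline).** Shrinkage to 21 mm meets PR (21/30 = 0.70). Regrowth to 30 mm is growth of 30/21 - 1 = 43% in diameter, or 1.43³ ≈ 2.9-fold in volume if all dimensions scale alike. Under the plan this is a 0% change and not progression. The plan calls progression at 1.2 × 30 = 36 mm; the smallest-size rule calls it at 1.2 × 21 = 25.2 mm.

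**Direction.** If the planning CT counts as one of the measurements, the smallest size cannot exceed baseline. So 1.20 × smallest ≤ 1.20 × baseline, and the plan's event can never come before the smallest-size event. Measured local control is therefore equal or higher under the plan, and equal when the tumor never shrank.

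**Reach.** Each patient whose status changes moves a crude rate in 20 patients by 1/20 = 5 percentage points. How many would change cannot be derived: the documents give no unresected fraction and no distribution of shrinkage or regrowth.

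**The case against.** The case for leaving the rule alone rests mainly on its limited reach, and much of that stands.

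- **Few patients may be affected.** Section VIII expects every patient to reach surgery, and the Synopsis places surgery 4-6 weeks after SBRT. A reader might infer from the completion rule that up to 14 of 20 are exposed. That is the most non-completers the rule tolerates (20 - 6), not a forecast, and a non-completer is not necessarily unresected: an R2 resection also fails completion. Section XI reports 11 of 36 patients initially deemed resectable as unresectable at exploration (31%, or about 6 of 20). Those were metastatic findings in a cohort not described as having had SBRT, so the figure does not transfer.
- **The analysed endpoint may not use this rule.** Section IX leaves locoregional recurrence undefined, and Section XII also allows PET/CT and the treating physician's judgement to enter. An earlier call is possible. But no criterion is given for either route, so the 20% CT rule is the only quantitative definition in the plan.
- **A delay in months is not in the documents.** A reader might infer that progression is called 5-10 months late. That needs an assumed volume doubling time (VDT) of 100-200 days, steady exponential regrowth and a full 30% shrinkage: 3 × VDT × ln(1/0.70)/ln 2 = 1.54 × VDT = 154-309 days. With 10% shrinkage the same formula gives 0.46 × VDT, or 46-91 days.
- **The wording of size is a lesser matter.** PD is above 20% in longest diameter, while local progression is 20% or more in unspecified size. A reader might take size as volume, where 20% is about 6% in diameter (1.2^(1/3) = 1.063). Volume is nowhere named as a response measure, and that reading would trigger progression earlier and reduce the problem.
- **A smallest-size reference has its own error.** The minimum of repeated measurements is pulled down by measurement noise. From 15 mm, a 3 mm change would count as progression. This objection stands, and the fix has to meet it.

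**Conclusion.** The point holds as a defect in a stated definition. Section XII measures local progression, and by its general comparison rule PD, from the planning CT at every visit. In unresected patients who shrink and then regrow, the required regrowth is 33% after 10% shrinkage and 71% at the PR threshold, and a partial responder back at its original size is scored as not progressed. The direction is certain relative to a plain smallest-size reference; the amount in the reported rate is unknown. The documents therefore do not support saying that the trial's local control will be overstated by any particular figure, or that it will be overstated at all if every patient is resected.

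The result rests on longest diameter being the measure and on the Section XII rule being what Section IX counts as a local event in unresected patients. Duration of response inherits the rule directly. Both outcomes are secondary and descriptive. The primary toxicity endpoint, the stopping rules and the decision on a phase II study do not use local progression. The change is worth making because it is cheap and the objective is named, not because the trial's main conclusion depends on it.

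**What to change.** In Section XII, for unresected patients, define local progression and PD identically: an increase of at least 20% in longest diameter over the smallest on-study measurement, with the planning CT counted among those measurements, plus a minimum absolute increase that the investigators state in advance. Say that reappearance of a lesion that had disappeared counts, since a percentage over zero is undefined. Keep the planning CT as the reference for CR and PR.

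In Section IX, Supplementary Analysis Plans, state that this definition is the local event for unresected patients and that new local disease on imaging is the local event after resection, where a percentage change in a removed lesion cannot be applied.

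The cost is a few sentences; the scans and measurements stay the same. Reported local control may be slightly less favourable. Some false progression calls from measurement error remain possible. The minimum absolute increase limits them, at the price of a later call for very small lesions.
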